As mentioned above, meta-analyses, including a recent Cochrane review, show valproate is potentially effective with a moderate to large effect size. However, the Cochrane review identifies several major limitations: most of the trials are low quality, conducted in very different healthcare settings to the UK, and none has measured quality of life or outcomes beyond 3 months. This means it is not clear if it is effective, or cost-effective in the NHS. There is, thus, clinical equipoise and considerable NHS costs associated with valproate augmentation of antipsychotic treatment in schizophrenia. This indicates the need for a high quality long-term double-blind RCT of valproate in the UK to determine its efficacy and cost-effectiveness.

To address this, our study design is a pragmatic 12-month, parallel group, placebo-controlled double-blind randomized controlled trial of augmenting existing AP treatment with valproate in patients (men and women, above 18 years of age) who fulfil DSM-5 criteria for schizophrenia or schizoaffective disorder and have persistent psychotic symptoms despite adequate (non-clozapine) AP treatment. Patients will be randomised 1:1 to either placebo + continuing antipsychotic treatment arm or valproate + continuing antipsychotic treatment arm. Randomisation will be stratified by diagnosis, sex and site. Valproate will be started at 500mg/day and titrated up to a dose of approximately 15 to 30 mg/kg/day of valproate over two weeks, in line with evidence that this dose range may be effective [18]. The placebo group will receive a matching placebo titration. To ensure treatment is optimised for each patient, and to promote retention in the trial, further dose increments or decrements will be allowed in both arms providing the dose does not exceed 2500mg/day.

The primary outcome is psychotic symptom severity after 12 months, measured using the PANSS positive subscale. Our secondary outcome measures include discontinuation rates, changes in clinical global impression scale (CGI-SCH), the development of adverse effects, cost-effectiveness and quality of life. Cost-effectiveness will be assessed using the Client Service Receipt Inventory; symptom severity will be assessed using the PANSS positive subscale; and quality of life will be assessed using the quality-adjusted life years (QALYS).

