4.2 Trial Design

This multi-site study will use a two-arm, randomized, double blinded, placebo-controlled trial using an intention to treat analysis (ITT). Patients with a diagnosis of schizophrenia or schizoaffective disorder on an antipsychotic (non-clozapine) for at least 6 weeks, continuing to have positive psychotic symptoms, will be randomised 1:1 to either placebo + continuing antipsychotic treatment arm or valproate + continuing antipsychotic treatment arm (Flow diagram). Randomisation will be stratified by sex, diagnostic category (schizophrenia or schizoaffective) and site and both in-patient as well as outpatients will be eligible to participate.

Patients must be on one or more non-clozapine oral antipsychotic for at least 6 weeks and should be on a stable dose for at least 2 weeks preceding the screening visit. In case of depot the dose must be stable for at least 2 treatment cycles or at least 30 days (whichever is longer) prior to the screening visit. During the trial, clinicians will also be able to adjust the antipsychotic dose, change formulation, change antipsychotics or even add if needed as this is a pragmatic trial. The addition or change of antipsychotic to clozapine will however be considered as discontinuation of the intervention and patients will be withdrawn from the study medication after down titrating their treatment. All subjects will receive follow-up assessments, including those who discontinue the study medication.

The trial will include a titration phase for the study medication lasting for approximately 2 weeks followed by a maintenance phase for the remaining 50 weeks of the study. At the end of the 52-week treatment period, subjects will be down titrated over 2 weeks. Outcomes will be measured at 3, 6 and 12 months using standard rating scales and after patients have finished the medication phase, follow up study indices will be obtained using electronic health records till the end of the study.

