6.4 Randomisation Procedure / Code Break

6.4.1 Randomisation

Randomisation will be undertaken by the local research team at each site once written informed consent has been obtained, eligibility confirmed, and baseline data collected. Randomisation will be stratified by diagnosis, site and sex and a permuted block randomization will be used for each stratum.

Randomisation will be performed via a bespoke web-based randomisation system hosted by the KCTU. This system can be accessed 24 hours a day. Authorised site staff will be allocated a username and password for the system by the Trial Manager. Authorised staff will log in and enter key information about the patient, including the unique Patient Identification Number (PIN). Once a patient is randomised, confirmation emails will be generated automatically, and appropriate information will be sent to relevant personnel.

The unique treatment pack numbers, batch numbers, expiry dates and last dispense dates for the study drugs will be uploaded into the KCTU Randomisation and Intervention Management System. The system will record the packs delivered to specific site pharmacies and will only allocate treatment packs that are available at that site to participants that are randomised there.

The investigator, research team, pharmacy and the trial manager will be kept blind to treatment allocation.

The system is also programmed to generate a schedule of each participants visit timeline for the entire study, to be sent within the randomisation email. A standard

feature is the ability to download automatically generated recruitment graphs of overall recruitment against target recruitment. The system is tested before the study begins. The system is also programmed to perform validation checks, such as checking for duplicate Participant Identification Numbers and preventing randomisation from proceeding in such cases.

Data will be exported upon request and passed to the trial statistician. Data may be exported in blinded, subgroup blinded, or unblinded formats.

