10.1 Sample Size

We have powered our study on the basis of superiority of valproate compared to placebo on the PANSS positive subscale using an effect size of 0.3. An effect size of 0.3 was selected as, in line with other trials of antipsychotic augmentation for treatment resistant schizophrenia, effects smaller than this are considered unlikely to be clinically meaningful [51, 52]. Assuming a two-sided significance level of 0.05 and 1:1 allocation, we will require 290 participants in the analysis dataset to detect an effect size of 0.3 with 90% power. This allows for a correlation between measures (at baseline and three follow-up points) of 0.4. An estimate of attrition of 20% across both arms for the primary end-point at 12 months requires a recruitment total of 362 participants at

baseline. The attrition rate of 20% is an estimate based on studies of antipsychotic augmentation using a similar design to our proposal, for example, the FOCUS study (Cognitive therapy augmentation of an antipsychotic for treatment resistance) had an attrition rate of ~10% over 21months [53] and the CHAT study (antipsychotic augmentation with a second antipsychotic) had an attrition rate <10% [54]. In this context, a study of a novel drug as an augmentation agent to antipsychotic treatment had a discontinuation rate of 29% at 12 months [55]. This study had a considerably larger burden of measures and higher levels of monitoring than our study. As such we expect our attrition and discontinuation rates to be in the range of 10-20% level in line with the other studies.

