10.2 Randomisation

Randomization will be stratified by diagnosis (schizophrenia or schizoaffective), site and sex and a permuted block randomization will be used for each stratum.

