10.3 Analysis

Statistical analysis will be done according to the predefined statistical analytical plan (SAP). There is no planned interim analysis unless the DMEC direct us to conduct one. Any deviations will be reviewed by the trial steering committee.

Statistical analysis

The primary analysis will use intention-to-treat principles by including all participants with outcome data in the arms to which they were randomized and follow the CONSORT 2010 statement. Baseline data will be presented using summary statistics with no testing for baseline differences. Treatment effects on the primary and secondary continuous outcomes will be estimated using linear mixed models fitted to outcome variables at all-time points. Fixed effects will be: diagnosis (schizophrenia/ schizoaffective); centre; baseline PANSS psychotic symptom severity rating; treatment; time (categorical); and time*treatment interactions. Marginal treatment effects will be estimated for outcomes at each time point and reported separately as adjusted mean differences in scores between the randomised groups with 95% confidence intervals and two-sided p-values. For binary outcomes, the same approach will be followed using logistic mixed models. All models will be estimated using maximum likelihood estimation, which allows for missing outcome data under the Missing At Random assumption. We may also use inverse probability weighting or multiple imputation to adjust for non-adherence to allocated treatment and other intermediate outcomes as predictors of future loss to follow-up.

Secondary analysis will include accounting for treatment switches from placebo to valproate arms using inverse probability of censoring weighting to estimate the average

treatment effect and longitudinal instrumental variable analysis to estimate the complier average causal effect.

Cost effectiveness evaluation

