For the base-case models under both perspectives, we will compare costs and outcomes between the treatment arms at baseline, 3-month, 6- month and 12-months follow-up. In these models we will control for baseline costs (only in the cost analysis); centre; baseline PANSS psychotic symptom severity rating; treatment; time (categorical); and time*treatment interactions.

Bootstrapping with mixed effects models will be used to generate confidence intervals that can be used to capture parameter uncertainty around the estimates in the cost-

effectiveness analysis. The 1000 treatment effect replications from this bootstrapping process will be plotted on cost-effectiveness planes and used to construct cost-effectiveness acceptability curves (CEAC). We will use cost effectiveness acceptability curves (CEACs) to explore the nature of the trade-off faced by the decision-maker in situations where one treatment option is both more effective and costly than the other. In this case, the decision maker would need to consider if it is worth incurring the higher costs to improve outcomes. Using this approach, we will be able to show the likelihood of valproate plus continuing antipsychotic treatment arm being seen as cost-effective relative to the placebo plus continuing antipsychotic treatment arm given different (implicit monetary) values placed on incremental outcome improvements. Bootstrapping and regression analysis will be used to generate CEACs. We will also explore the sensitivity of the results to changes in key parameters and the analyses will be repeated. This will include the same control variables as those in the base-case model.

11 Trial Steering Committee

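### Randomisation is stratified by sex, but the listed fixed effects of the linear mixed models leave sex out; the effect is small and conservative

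*Protocol*

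**What the plan says.** Four places in the protocol name the same three stratification factors:

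- Background & Rationale, under Rationale: "Randomisation will be stratified by diagnosis, sex and site".
- Section 4.2: "Randomisation will be stratified by sex, diagnostic category (schizophrenia or schizoaffective) and site".
- Section 6.4.1: "Randomisation will be stratified by diagnosis, site and sex and a permuted block randomization will be used for each stratum".
- Section 10.2: "Randomization will be stratified by diagnosis (schizophrenia or schizoaffective), site and sex and a permuted block randomization will be used for each stratum".

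Section 10.3 specifies the model for the primary and secondary continuous outcomes as a closed list: "Fixed effects will be: diagnosis (schizophrenia/ schizoaffective); centre; baseline PANSS psychotic symptom severity rating; treatment; time (categorical"), and last the time-by-treatment interaction. Binary outcomes follow the same approach with logistic mixed models.

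The cost-effectiveness part of section 10.3 gives the base-case controls as baseline costs (in the cost analysis only) and then "centre; baseline PANSS psychotic symptom severity rating; treatment; time (categorical); and time*treatment interactions". That list has neither sex nor diagnosis.

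**The concern.** Blocking within sex makes the arms nearly equal in their proportions of men and women. That balance removes a source of chance variation from the treatment comparison. A model without sex does not know this: it leaves the variation due to sex in the residual and computes the standard error as if sex could have been imbalanced. If sex is prognostic, the reported interval is wider than the design warrants and the test rejects less often than its nominal level.

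Two of the three design factors are already in the list, so the absence of sex looks like an oversight. The protocol fixes the list itself. A statistical analysis plan that copies the list carries the omission forward, and one that adds sex departs from the protocol text. Adding sex after unblinding would be open to criticism as a post hoc choice.

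**Working it through.** **1. Compare the lists.** Stratification factors: diagnosis, site, sex. Design factors in the clinical model: diagnosis, centre. Missing: sex. Design factors in the base-case economic models: centre. Missing: sex and diagnosis.

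**2. The plan's own sample size, for the baseline of the power figures.** Inputs from section 10.1: effect size 0.3, two-sided 0.05, 1:1 allocation, 90% power, correlation 0.4, three follow-ups, 290 analysed (145 per arm), 20% attrition.

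- Per arm, n = 2 × ((1.96 + 1.2816)/0.3)² × f, where f is the variance factor.
- f = (1 + 2 × 0.4)/3 = 0.60 (mean of three follow-ups) gives 282 in total, close to 290; 145 per arm then has 91.0% power.
- f = 1 − 0.4² = 0.84 (one time point, baseline-adjusted) gives 79.6% power at 145 per arm.
- 290/0.80 = 362.5, matching the 362 recruited.

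Both values of f are carried forward, so that the effect of omitting sex can be seen under either reading.

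**3. Effect of omitting sex from a linear model.** Let R² be the share of *residual* variance, after baseline PANSS positive score, diagnosis and centre, that sex explains. The protocol gives no figure, so 1%, 2% and 5% are assumed. With sex exactly balanced:

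- standard error overstated by the factor 1/√(1 − R²);
- actual type I error = 2 × (1 − Φ(1.96/√(1 − R²))).

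Exact balance will not survive attrition. If dropout is random at 20%, about 20% of the chance imbalance returns, and R² is replaced by 0.8 × R² in both formulas.

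| R² (assumed) | SE inflation, exact balance | Type I, exact balance | SE inflation, 20% random dropout | Type I, 20% random dropout |
|---|---|---|---|---|
| 1% | 0.5% | 4.89% | 0.4% | 4.91% |
| 2% | 1.0% | 4.77% | 0.8% | 4.82% |
| 5% | 2.6% | 4.43% | 2.1% | 4.55% |

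**4. Power at 145 per arm, exact balance.** The model's standard error is √(2f/145), and the true one is √(2f(1 − R²)/145).

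- Sex omitted: power = Φ((0.3 − 1.96 × model SE)/true SE).
- Sex included: power = Φ(0.3/true SE − 1.96).

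Example with f = 0.84 and R² = 5%: model SE 0.1076, true SE 0.1049. Omitted: Φ((0.3 − 0.2110)/0.1049) = 80.2%. Included: Φ(2.860 − 1.96) = 81.6%.

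| R² | f = 0.84: omitted / included | f = 0.60: omitted / included |
|---|---|---|
| 1% | 79.7% / 80.0% | 91.1% / 91.2% |
| 2% | 79.8% / 80.4% | 91.2% / 91.5% |
| 5% | 80.2% / 81.6% | 91.5% / 92.3% |

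With f = 0.84 the loss is about 0.3 to 1.4 points; with f = 0.60 it stays below 1 point. These results are analytic.

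**The case against.** The strongest reply is that no conclusion of the trial is likely to turn on this. The 5% level is protected, the treatment effect is not biased, and the power at stake is around a point. The input that drives the size is assumed. Any sex difference already visible in baseline PANSS is largely absorbed by that covariate, and attrition loosens the balance. All of this stands, and it is why the figures are given as upper values on residual variance.

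The protocol also defers to a statistical analysis plan that is not shown and may include sex. That does not remove the point, because section 10.3 states an explicit list.

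Three stronger readings are tempting and are not supported:

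- *The primary test is invalid or biased.* Sex is balanced by design, and the error runs in the conservative direction.
- *The omission aggravates a trial with only about 80% power.* Whether 145 per arm gives 80% or 90% depends on how the repeated measures enter the sample size calculation. That is a separate question: omitting sex does not cause the gap, and adding sex barely changes it.
- *The same error figures hold for every model in section 10.3.* The standard-error argument is for linear models. In a logistic model, adding a prognostic covariate changes the odds ratio being estimated and need not shrink its standard error. The economic analysis reports bootstrap intervals and acceptability curves and has no 5% test, and its covariates must differ from the clinical ones anyway because baseline cost enters only there. For these models the case rests on consistency with the design alone.

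**Conclusion.** The mismatch is certain from the text: sex is a stratification factor in four places and is absent from the listed fixed effects. Its consequence is minor. For assumed residual shares of 1%, 2% and 5%, standard errors are too large by at most about 0.5%, 1.0% and 2.6%, and type I error is about 4.9%, 4.8% and 4.4–4.6%. The power loss is roughly 0.3 to 1.4 points at 145 per arm. If sex is not prognostic given the other covariates, the loss is nil. The figures assume a linear model and exact sex balance, except that the upper end of the 4.4–4.6% range allows for 20% random dropout. The change is worth making because it costs almost nothing and brings the model into line with the design; the primary analysis is not in doubt.

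**What to change.** Add sex to the fixed effects of the linear mixed models in section 10.3, or state why it is left out. Use one term, site or centre, for the same factor throughout.

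For consistency with the design, also add sex to the logistic mixed models, noting that the odds ratio is then conditional on sex and that no gain in precision is promised. Add sex and diagnosis to the base-case cost and outcome models.

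The cost in the linear model is one degree of freedom and a few words of text. Sex is already recorded at screening and is needed for randomisation, so no new data are required, and the sample size does not change. The change should be made before unblinding.

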4.1.2 Secondary outcomes

The main secondary outcome will be PANSS positive score difference at 3 months.

Other secondary outcome measures include:

- PANSS positive score at 6 months
- Total symptoms measured using the PANSS at 3, 6 and 12 months.
- Change in PANSS Factor scores from baseline derived from the PANSS scores at 3, 6 and 12 months, an approach used for minimizing pseudospecificity of treatment effects [30].
- Change in Clinical Global Impression scale (Schizophrenia version). This is a brief, stand-alone assessment of a clinician's overall view of the severity of the patient's illness that is designed to identify a clinically significant change prior to and after initiating a medication. It will be carried out at baseline, 3, 6 & 12-month follow-up visits [31].
- Aggression levels will be measured using the Modified Overt Aggression Scale (a brief four category scale to measure aggression in clinical settings. It will be carried out at baseline, 3, 6 & 12-month follow-up visits [32].
- Depression will be measured using the Calgary depression scale for schizophrenia (CDSS) at baseline, 3, 6 & 12-month follow-up visits [33].
- Young's Mania rating scale (YMRS) will be measured at baseline, 3, 6 & 12-month follow-up visits [34]. YMRS is one of the most frequently utilized rating scales to assess manic symptoms.
- Body mass index will be determined at the 3, 6 & 12-month follow-up visits as valproate has the potential for inducing weight gain.
- Patient reported outcomes will be evaluated using the Short Warwick-Edinburgh Well-being scale (SWEMWBS). It will be measured at the 3, 6-month and 1-year time points [35].

- Cost effectiveness will be assessed using measures collected at baseline, 3, 6 & 12-month follow-up visits: the Client Service Receipt Inventory (CSRI) [36], PANSS and the 36-item short form health survey (SF-36)[37]. Adverse effects will be assessed at baseline, 3, 6 & 12-month follow-up visits. We will use the UKU side effect rating scale, a clinician observed rating scale for psychotropic drugs [38]. The Udvalg for Kliniske Undersogelser (UKU) Side Effect Rating Scale evaluates 48 symptoms in 4 categories; psychic, autonomic, neurologic, and other. Using a combination of interview and physical examination, clinicians will assess the magnitude of symptoms, perceived causality and degree of disability.

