8.1.2 Secondary Efficacy Parameters

PANSS positive subscale and total scores

PANSS is a clinician-rated scale that measures symptom severity in schizophrenia. PANSS total score (including positive subscale) will be measured at baseline, 3, 6 and 12-month time points to measure treatment outcomes.

PANSS Factor score

Transformed PANSS factors intended to reduce pseudospecificity among symptom domains and enhance understanding of symptom change in antipsychotic-treated patients with schizophrenia will be analysed [30]. A significant impediment to correctly characterizing the efficacy of new treatments is the extent to which PANSS factors are correlated with each other. As a consequence, it is difficult to determine whether improvement in the severity of symptoms in PANSS is a domain-specific treatment effect or is a nonspecific effect secondary to observed improvement in correlated PANSS items. Hence this factor analysis approach at the 3, 6 and 12-month time point will help us understand the symptom change related to the adjunctive treatment. Data needed to do the factor analysis will be obtained from PANSS interviews.

CGI (Schizophrenia version)

The CGI-SCH scale is a valid, reliable instrument to evaluate severity and treatment response in schizophrenia [30]. Given its simplicity, brevity and clinical face validity, the scale is appropriate for use in observational studies. It consists of only two categories; severity of illness and degree of change. The severity of illness category evaluates the situation during the week previous to the assessment, while the degree of change category evaluates the change from the previous evaluation (or from the phase preceding the treatment trial). Each category contains five different ratings (positive, negative, depressive, cognitive and global) that are evaluated using a seven-point ordinal scale. Change from baseline will the parameter that will be analysed. It takes approximately 10 minutes to complete this instrument.

Modified Overt Aggression Scale (MOAS)

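### Section 10.3 adjusts the clinical secondary outcomes other than PANSS positive for baseline PANSS positive, not for their own baseline: a loss of precision that costs nothing to remove

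*Protocol*

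**What the plan says.** Protocol section 10.3 applies one model to all continuous outcomes: "Treatment effects on the primary and secondary continuous outcomes will be estimated using linear mixed models fitted to outcome variables at all-time points". The fixed effects are then given as a definite list: diagnosis, centre, and "baseline PANSS psychotic symptom severity rating; treatment; time (categorical); and time*treatment interactions". No other baseline measurement appears in it.

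Two secondary outcomes are defined as change. Section 4.1.2 defines the PANSS factor scores as change from baseline, and section 8.1.2 says of CGI-SCH: "Change from baseline will the parameter that will be analysed". Neither section says that the baseline value also enters as a covariate.

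The outcomes' own baselines are available. Section 7.1 lists PANSS, CGI-SCH, CDSS, YMRS, MOAS and SWEMWBS at Visit 2, and Table 1 has height, weight and BMI at screening and again at baseline.

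The list does suit some secondary outcomes. Section 4.1.2 states: "The main secondary outcome will be PANSS positive score difference at 3 months". For that outcome, and for PANSS positive at 6 months, baseline PANSS positive is the outcome's own baseline. The cost-effectiveness part of section 10.3 controls for baseline costs in the cost analysis and provides a baseline adjustment for QALYs.

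**The concern.** In a randomised comparison of a continuous outcome, the most useful covariate is usually that outcome's own baseline value. Here the list appears to have been written for the primary outcome and then extended to the secondary ones. A depression, mania or well-being score would be adjusted for the baseline of a different scale, while its own baseline lies unused in the database.

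For the change-score outcomes the baseline is used, but only by subtraction. Subtraction removes too much of the baseline when the correlation with follow-up is below 1, and the remaining noise is what adjustment for the own baseline would remove.

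At stake is the width of the confidence intervals for these outcomes, and how far a chance difference between the arms in an outcome's own baseline carries through to its estimate. BMI is among them, and the protocol includes it because valproate may cause weight gain.

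**Working it through.** **Inputs from section 10.1.** Two-sided 5% level, equal arms, standardised difference 0.3, power 90%, 290 analysed, 20% attrition, 362 recruited. On the correlation the section says: "This allows for a correlation between measures (at baseline and three follow-up points) of 0.4". That value is given in the PANSS positive calculation. The protocol gives none for any other scale.

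**The plan's own figure.** For two means with standardised difference 0.3, the number per arm is 2 × ((1.960 + 1.282)/0.3)² = 233.5, multiplied by a variance factor.
- Single follow-up without baseline: factor 1, so 234 per arm, 468 in total.
- Single follow-up adjusted for own baseline: factor 1 − 0.4² = 0.84, so 394 in total.
- Mean of three follow-ups without baseline: factor (1 + 2 × 0.4)/3 = 0.6, so 282 in total, within 3% of 290.

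The stated 290 is therefore close to the mean-of-three calculation. For attrition, 290/0.8 = 362.5, against 362 stated. This only establishes the 290 and the 0.4 used below; the sample-size basis is a separate matter.

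**Variance of one follow-up contrast.** Take equal variances at baseline and follow-up, scaled to 1, complete data, and baseline to follow-up correlation ρ.
- Follow-up score without own baseline: 1.
- Change score without own baseline as covariate: 2(1 − ρ).
- Either one with own baseline as covariate: 1 − ρ².

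At ρ = 0.4 these are 1.00, 1.20 and 0.84.
- Loss for a score: 1 − 0.84/1.00 = 16%, so 290 patients are worth 290 × 0.84 = 244. The confidence interval is √(1.00/0.84) = 1.09 times as wide.
- Loss for a change score: 1 − 0.84/1.20 = 30%, so 290 are worth 290 × 0.70 = 203. The interval is √(1.20/0.84) = 1.20 times as wide.

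Both figures suppose that baseline PANSS positive explains nothing of the other outcome, so they are upper limits at this ρ.

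**Allowing for the covariate that is planned.** Let baseline PANSS positive correlate r with the outcome's own baseline and act on follow-up only through it (assumption). The planned analysis then has variance 1 − (ρr)² for a score and 2(1 − ρ) − r²(1 − ρ)² for a change score. At ρ = 0.4:

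| r | score variance | loss, score | change variance | loss, change |
|---|---|---|---|---|
| 0 | 1.000 | 16.0% | 1.200 | 30.0% |
| 0.3 | 0.986 | 14.8% | 1.168 | 28.1% |
| 0.5 | 0.960 | 12.5% | 1.110 | 24.3% |
| 0.7 | 0.922 | 8.9% | 1.024 | 17.9% |
| 0.8 | 0.898 | 6.4% | 0.970 | 13.4% |

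High r is the relevant end for PANSS total, which contains the positive subscale. For PANSS positive itself r = 1 and the loss is 0.

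**Allowing for another ρ.** Upper limits (r = 0) are ρ² for a score and 1 − (1 − ρ²)/(2(1 − ρ)) for a change score:

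| ρ | score | change |
|---|---|---|
| 0.3 | 9% | 35% |
| 0.4 | 16% | 30% |
| 0.5 | 25% | 25% |
| 0.6 | 36% | 20% |

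**The case against.** **The SAP may settle this.** Section 10.3 refers to a predefined SAP, and the list may be shorthand for the primary outcome. But the sentence names the secondary continuous outcomes, and the list is definite. Where the authors wanted another baseline, for costs and QALYs, they said so. This is a stated choice, not an omitted detail.

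**Baseline may enter as an outcome.** If all time points were read to include baseline, the model would still have a free treatment effect at baseline. With complete data, the follow-up contrasts would then not be adjusted for own baseline.

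**The size is uncertain.** This stands. The 0.4 belongs to PANSS positive, and the planned covariate recovers part of the loss, so 16% and 30% must be given as upper limits.

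A reader might infer more than the documents support:
- That every secondary outcome is affected. PANSS positive at 3 months (the main secondary outcome) and at 6 months, costs and QALYs are not. Nor does the protocol define a continuous UKU total: section 9.1 describes 48 items, each scored 0 to 3.
- That a change score is always worse than ignoring baseline. Without help from PANSS positive this holds only for ρ below 0.5, because 2(1 − ρ) exceeds 1 only there.
- That the argument covers all of CGI-SCH. Its degree-of-change category is rated directly as change, so only the severity category has a baseline value to adjust for.
- That BMI loses a particular, larger amount. No correlation for BMI is given, so no figure is put on it.
- That the estimates are biased. With complete data, randomisation protects them whichever baseline is used. With dropout, including the own baseline makes the missing-at-random assumption easier to defend, but the documents do not show that leaving it out causes bias.

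**Conclusion.** The point holds for the continuous clinical secondary outcomes other than PANSS positive: PANSS total, PANSS factor scores, CGI-SCH severity, MOAS, CDSS, YMRS, SWEMWBS and BMI. As section 10.3 is worded, their models omit a baseline that the trial collects.

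At a correlation of 0.4 the loss of effective sample is about 6% to 16% for follow-up scores and 13% to 30% for change scores, as the correlation between baseline PANSS positive and the outcome's own baseline runs from 0.8 down to 0. Over correlations of 0.3 to 0.6 the upper limits are 9% to 36% for scores and 20% to 35% for change scores. These figures rest on equal variances at baseline and follow-up, complete data and, for the lower ends at 0.4, on PANSS positive acting only through the own baseline.

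The harm is wider intervals for lower-ranked outcomes. The primary and main secondary analyses are unaffected, and the protocol makes no power claim for the affected scales. This is a free improvement, not a threat to validity.

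**What to change.** In the fixed-effects list of section 10.3, replace the baseline PANSS psychotic rating with the baseline value of the outcome being analysed. For the PANSS positive outcomes this is still baseline PANSS positive, so the primary model does not change. State that the covariate stays in the model where change from baseline is reported (PANSS factors, CGI-SCH severity); the treatment difference is then the same whether the follow-up score or the change is modelled.

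The cost is one line of protocol text, carried into the SAP and settled before unblinding. No new data, visits or patients are needed.
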